6.2.5 Missing Last Dates of Study Drug Dosing

Missing dates for study drug dosing will not be imputed.

6.2.6 Missing Diagnosis Dates

If the month and year are present but the day is missing, the diagnosis date will be set to first day of the relevant month. If only the year is recorded the diagnosis date will be set as “01-Jan” for that year.

6.2.7 Exposure to Study Drug

Exposure to study drug will be calculated as the date of last dosing minus the first day of dosing + 1. The exposure calculation will not take into account breaks in therapy.

6.2.8 Inexact Values

In the case where a variable is recorded as “> x”, “ \geq x”, “< x” or “ \leq x”, a value of x will be taken for analysis purposes.

For pharmacokinetic data values below lower limit of quantification (LLOQ) will be handled as follows in summary tables:

- If value collected before first dose of study treatment then set to 0.
- If value collected on or after the first dose of study treatment then set to LLOQ/2.

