#### **8.5 Day 3, Day 9, and Day 15**

The following additional assessment will be conducted on Days 3, Day 9 and 15:

1. SpO2 level (%) (or day of discharge if prior to Day 15)
2. Serum Chemistry – ([Appendix A](#)) (or day of discharge if prior to Day 15)
3. Hematology – ([Appendix A](#)) (or day of discharge if prior to Day 15)
4. Viral load (Day 9 only or day of discharge if prior to Day 9)
5. WHO Ordinal Scale score assessment (Day 15 only or day of discharge if prior to Day 15)
6. Physical examination (including weight) (Day 15 only or day of discharge if prior to Day 15)
7. Pregnancy test (Day 15 only or day of discharge if prior to Day 15) (women of childbearing potential only)
8. 12 lead ECG (single) (Day 15 only or day of discharge if prior to Day 15)
9. Plasma samples for pharmacokinetic assessment will be taken prior to dosing on Day 3 and Day 9.

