3.2 Secondary Endpoints

The secondary endpoints on this study are:

1. The proportion of subjects that are alive without respiratory failure at Day 15, Day 22, and Day 29. Day 29 is the key secondary endpoint. Respiratory failure is defined as endotracheal intubation and mechanical ventilation, extracorporeal membrane oxygenation, high-flow nasal cannula oxygen delivery, noninvasive positive pressure ventilation, clinical diagnosis of respiratory failure with initiation of none of these measures only when clinical decision making is driven solely by resource limitation.
2. Days in ICU
3. WHO Ordinal Scale for Clinical Improvement change from baseline to Day 15, Day 22, and Day 29
4. Days on mechanical ventilation
5. Days in hospital
6. Proportion of subjects that die on study at Day 15, Day 22, and Day 29.
7. Change from baseline in viral load (baseline to Day 9)

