6.11 Efficacy Analyses

All statistical tests will be performed using a two-tailed 5% overall significance level, unless otherwise stated. All comparisons between treatments will be reported with 95% confidence intervals for the difference.

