6.11.5.1 Change from baseline in viral load (baseline to Day 9)

Descriptive statistics (n, mean, standard deviation, median, minimum and maximum) will be summarized for absolute values and change from baseline by treatment group and visit. For viral load post-BL time points for summary and analysis will be 'Last On-Study' and 'Day 9 only'.

Change from baseline in viral load will be analyzed using the same methodology as for 'Days in ICU' but including also viral load at baseline as covariate.

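### The SAP analyses a viral load recorded as `< x` as exactly x; on a log10 scale this can shrink a true treatment difference and make its confidence interval under-cover

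*SAP*

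**What the plan says.** SAP 6.2.8 (Inexact Values) covers any variable recorded as `> x`, `>= x`, `< x` or `<= x`: "a value of x will be taken for analysis purposes". The one exception reads "For pharmacokinetic data values below lower limit of quantification (LLOQ) will be handled as follows in summary tables": zero before the first dose, half the LLOQ on or after it.

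Change in viral load from baseline to Day 9 is the last of seven secondary endpoints (SAP 3.2; Protocol 5.3.2). Its analysis is in the SAP section at the end of 6.11.5, headed 6.11.5.1, a number also used for the respiratory-failure endpoint. That section borrows its model from another endpoint, days in ICU: "Change from baseline in viral load will be analyzed using the same methodology as for". The baseline value is added to the covariates. The days-in-ICU method (SAP 6.11.5.2) is a linear ANCOVA with study site (or country or region), remdesivir use, dexamethasone use and WHO stratum. Two post-baseline time points are analysed: the last on-study value and Day 9 only.

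SAP 6.11 promises a 95% confidence interval for every treatment comparison. Neither the SAP nor Protocol 9.5.1.5 gives an assay, unit, limit of quantification, coding for an undetectable result, or analysis scale for viral load.

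**The concern.** A result below the limit is left-censored: the true value lies somewhere under the limit, and these are the best virological outcomes. Scoring them at the limit caps the fall that can be observed. If VERU-111 lowers viral load, more of its subjects reach the cap, and the arms are pulled together. The cap also compresses the residual variance, so the interval is both displaced and too narrow.

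The SAP recognises the problem for descriptive PK summaries but not for an efficacy endpoint compared between arms. At stake is the estimate and interval for the trial's only direct measure of antiviral activity, which is part of the rationale in Protocol 3.1. The mortality analysis is not affected.

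**Working it through.** The documents state no viral-load figure, so there is none to reproduce. The size has to be found by simulation under stated assumptions.

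**From the documents:** 140 and 70 subjects (SAP 4); two-sided 5% level (SAP 6.11); values below limit L set to L (SAP 6.2.8); ANCOVA adjusted for baseline viral load. Site, remdesivir, dexamethasone and WHO stratum were left out of the simulated models.

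**1. Log10 scale, first set of assumptions.** Baseline mean 5.5, SD 1.5; Day 9 placebo mean 3.2; slope on baseline 0.5; residual SD 1.3; true difference -0.60. Shrinkage = 1 - estimate/(-0.60); for example 1 - 0.43/0.60 = 28%.

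| Share of Day 9 values below limit | ANCOVA, values set to limit | Shrinkage | Coverage of 95% CI | Left-censored normal model |
|---|---|---|---|---|
| 12% | -0.54 | 10% | about 92% | about -0.60 |
| 30% | -0.43 | 28% | about 78% | about -0.60 |
| 42% | -0.36 | 40% | about 55% | about -0.60 |
| 55% | -0.29 | 52% | about 20% | about -0.60 |
| 68% | -0.21 | 65% | about 1% | about -0.60 |

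Coverage of the censored model was about 94-97%. Its power gain was modest: about 0.85 to 0.89 at 30% below the limit, and no more than about 0.08 anywhere.

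**2. Log10 scale, second set.** Baseline mean 6, SD 1.5; correlation 0.5 with Day 9; limit 10^2 or 10^3 copies/mL; 400,000 subjects, with z rescaled to 210. The pooled share is (2 x VERU-111 share + placebo share)/3.

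| Below limit, VERU-111 / placebo | Pooled | True difference | Fraction kept | z, true values to set-to-limit |
|---|---|---|---|---|
| 9% / 5% | 8% | -0.5 | 93% | 2.66 to 2.65 |
| 25% / 16% | 22% | -0.5 | 80% | 2.66 to 2.57 |
| 50% / 37% | 46% | -0.5 | 56% | 2.60 to 2.26 |
| 75% / 63% | 71% | -0.5 | 31% | 2.62 to 1.89 |
| 84% / 63% | 77% | -1.0 | 26% | 5.28 to 3.62 |

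The test loses less than the estimate because the substitution also reduces the variance. With a true difference of zero, the estimate stayed within 0.004 log10 of zero.

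**3. Half the limit instead.** At 50% / 37%, LLOQ/2 gives -0.321 against a true-value estimate of -0.499, so it keeps 0.321/0.499 = 64%, compared with 56% for the limit itself. It is better but still biased.

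**4. Untransformed scale.** Each substituted value moves by less than L, so, before adjustment for baseline, an arm's Day 9 mean moves by less than L times its share below the limit. With L = 1,000 and 75% / 63% below, the estimate goes from -67,010 to -66,890 copies/mL, a change of 120/67,010 = 0.2%. Under the first set of assumptions the rule keeps at least 99.88% of the estimate. Power of the untransformed ANCOVA there is about 0.2 with or without the rule, against 0.87-0.88 on uncapped log10 values.

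**The case against.** The strongest reply is that the SAP states no log transformation. Read literally, the analysis is on untransformed values, where the substitution changes almost nothing. That stands, and it rules out any claim that the harm is independent of scale. It does not rescue the plan: the literal analysis has power of about 0.2 under the same assumptions, and the obvious remedy, moving to log10, is what makes the substitution matter.

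A reader might also infer that every subject who cleared the virus is scored at the limit. The documents do not support this. The rule acts only on results recorded with an inequality sign. A result entered as negative, not detected or 0 is not covered, and the SAP gives no rule for it.

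Nor do the documents say that many Day 9 values will fall below the limit. With few below it, the loss is about 7-10% and coverage is close to nominal.

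The consequence is limited too. Viral load is outside the Holm family in SAP 6.11.7, which covers days in ICU and days on mechanical ventilation. The bias runs toward no effect and creates no false-positive risk. Finally, the censored model was tested on data generated as normal, which favours it; its recovery of -0.60 shows what is achievable when that assumption holds.

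**Conclusion.** The point holds conditionally. By its wording, SAP 6.2.8 reaches viral load, and nothing in the viral-load section overrides it. An understated difference requires three things: a true effect, below-limit results recorded as `< x`, and analysis on a log scale. Given those, the assumed inputs put the shrinkage at about 7-10% when about 7-12% of Day 9 values are below the limit, rising to about 65-75% at about 70% or more, with 95% coverage falling from about 92% to about 1% over the first table.

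A reader might go further and conclude that the planned estimate is certainly shrunk. The documents do not support that, because the scale, the assay limit, the coding of undetectable results and the share below the limit are all unstated.

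The change is still worth making: on either reading of the scale, a censored log10 analysis performs better than what is written. The gain is mainly in bias and interval coverage, for a secondary endpoint without an alpha-controlled claim.

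**What to change.** - In SAP 6.2.8, exempt viral load from the general rule.
- In the viral-load section, state the assay, its LLOQ, how undetectable results are recorded, and that analysis is on the log10 scale.
- Analyse post-baseline log10 viral load with a left-censored normal (Tobit) model, for example in PROC LIFEREG, with the planned covariates plus baseline log10 viral load. Enter results below LLOQ and undetectable results as censored at LLOQ.
- State how a below-limit baseline value enters as a covariate, for example as LLOQ plus a below-limit indicator. The general rule currently applies to baseline as well.
- Report the number and percent below LLOQ by arm beside the descriptive statistics.
- Keep ANCOVA on log10 values with LLOQ/2 as a sensitivity analysis only, since it remains biased.

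The cost is SAP wording and one procedure call, with no new data. The downside is that the censored model assumes approximately normal log10 values, which becomes harder to check as the share below the limit grows.

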6.2.9 Area under curve (AUC) of WHO Ordinal Scale for Clinical Improvement

Area under curve (AUC) of WHO Ordinal Scale for Clinical Improvement will be calculated from baseline up to Day 60 using trapezoidal rule. For each subject all available measurements up to

Controlled Quality Management Document	
	Sponsor: Veru Inc.
	Protocol Number: V3011902
STATISTICAL ANALYSIS PLAN. PHASE 2-3-4	

study day 60 are included in the calculations. If subject does not have record on Day 60 then the last observation carried forward (LOCF) will be used. If a patient dies on Day 10, then they would be an 8 from Day 10 to Day 60. If the patient is discharged as a 2 on Day 5 then they would be a 2 from Day 5 to Day 60. Actual collection times will be used in the calculations.

6.2.10 Discharge, Early Termination and Unscheduled Visits

Only scheduled post-baseline values will be tabulated. Discharge, early termination and unscheduled visits will be mapped to the closest scheduled post-baseline time point. If subject then having more than one record mapped for specific visit then the closest value to the scheduled time point will be used in the analysis.

All collected data will be presented in subject data listings.

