#### **8.6 Day 22 ± 3 days (these assessments will also be done at Early Termination from the study)**

The following assessments will be performed on Day 22 (± 3 days):

1. Vital Signs (temperature/pulse/supine blood pressure)
2. SpO2 level (%)
3. Physical examination (including weight)
4. 12-lead ECG (single)

5. Chest X-ray or CT scan
6. Clinical Laboratory tests
  - a. Hematology ([Appendix A](#))
  - b. Serum chemistry ([Appendix A](#))
  - c. Urinalysis
7. Adverse events
8. Pregnancy test (women of childbearing potential only)
9. Record the usage of any concomitant medications and ongoing treatments.
10. WHO Ordinal Scale score assessment (at Day 22 or day of discharge if prior to Day 22)

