6.11.5 Secondary Efficacy Analyses

6.11.5.1 The proportion of subjects that are alive without respiratory failure at Day 15, Day 22, and Day 29.

This analysis will compare subjects that are alive without respiratory failure on the visit (responder) to subjects who died before the visit or had respiratory failure (non-responder) on the visit.

Responders are subjects who are alive and have Grade 0-4 on the WHO Ordinal Scale for Clinical Improvement on the visit. If subject was discharged from the hospital prior to the visit and WHO Ordinal Scale for Clinical Improvement is not collected at the specific visit then the last available observation before or at the time of discharge will be used. If subject's vital status is not known then missing information will be imputed using multiple imputation.

Non-responders are subjects who died before the visit or has Grade 5, 6, 7, or 8 on the WHO Ordinal Scale for Clinical Improvement on the visit.

The number and percentage of responders will be summarized by treatment group and visit.

Responders will be analyzed using the same methodology as for the primary endpoint (separate analysis will be performed for each visit):

- Multiple imputation + logistic regression model

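### SAP 6.2.10 sets no distance limit when it maps early-termination and unscheduled WHO scores to a visit, and it is not reconciled with the imputation rule in SAP 6.11.5.1

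*SAP*

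**What the plan says.** **Mapping rule.** SAP 6.2.10 says that "Discharge, early termination and unscheduled visits will be mapped to the closest scheduled post-baseline time point". If more than one record then falls on a visit, "the closest value to the scheduled time point will be used in the analysis". The section gives no window and no rule for equal distances. It does not say whether the time points are those at which the particular measurement is scheduled or all study visits.

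**WHO score schedule.** The first post-baseline score is at Day 15 (Protocol 8.5: "WHO Ordinal Scale score assessment (Day 15 only or day of discharge if prior to Day 15"). Later scores are at Days 22, 29, 45 and 60, each ±3 days (Protocol 8.6 to 8.8). No window is given for Day 15. The Day 22 list includes a WHO score, and its section heading adds that "these assessments will also be done at Early Termination from the study", so a subject who terminates early should have a score on that day.

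**Missing data for alive without respiratory failure.** SAP 6.11.5.1 has two rules. A subject discharged before the visit is scored on the last value up to discharge. Otherwise, "If subject's vital status is not known then missing information will be imputed using multiple imputation".

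**Viral load.** Protocol 8.5 schedules one post-baseline sample: "Viral load (Day 9 only or day of discharge if prior to Day 9". The SAP's viral load section, also numbered 6.11.5.1, names two analysis time points, 'Last On-Study' and 'Day 9 only'.

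**The concern.** A mapping rule without a window turns a record from one time into an observed outcome at another. For a subject who has left the study, it puts status at departure in place of status at the visit, and the analysis then treats that value as data rather than as missing.

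WHO scores 0-4 count as response in SAP 6.11.5.1, and 4 is an allowed entry score (Protocol 6.2.1). A subject who enters at 4 and withdraws unchanged a few days later can therefore be counted as a Day 15 success. If early withdrawal, or the reasons for it, differ between arms, the Day 15 comparison is distorted, and the Day 29 comparison to a lesser degree. Two programmers could also build different datasets from the same text, because the term that decides the mapping is undefined.

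**Working it through.** The plan states no figure on this point, so there is none to reproduce. The check is which days reach which visit, and then which rule governs.

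**1. Nearest-visit ranges for the WHO score, read by parameter.** A record on day d goes to the visit v with the smallest |d − v|, so the boundary between neighbouring visits is their midpoint. For Days 15, 22, 29, 45 and 60 the midpoints are 18.5, 25.5, 37 and 52.5.

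| Visit | Days mapped | Within ±3 | Mapped but outside ±3 |
|---|---|---|---|
| 15 | 2-18 | 12-18 | 2-11 |
| 22 | 19-25 | 19-25 | none |
| 29 | 26-36 | 26-32 | 33-36 |

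The ±3 days is the protocol's window for Days 22 and 29; using it at Day 15 is an assumption. There, 10 of the 17 mapped days lie outside it. A Day 4 record is 15 − 4 = 11 days away. Day 37 is 8 days from both Day 29 and Day 45, and nothing resolves the tie.

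**2. The other reading.** If all of Days 3, 9, 15, 22, 29, 45 and 60 count as time points, the first midpoints are 6, 12 and 18.5. A Day 4 score then goes to Day 3, Day 15 takes only Days 13-18, and Days 6 and 12 are further ties. The Day 29 range stays 26-36, so the Day 33-36 excess arises under either reading. The parameter reading is the more natural one, because 6.2.10 opens by restricting tables to scheduled values and no WHO score is scheduled on Day 3 or Day 9.

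**3. One subject through the rules.** Take a subject with score 4 who terminates undischarged on Day 4, with no later WHO score. Under the parameter reading:

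- *Vital status unknown at Day 15.* SAP 6.2.10 supplies a responder; SAP 6.11.5.1 calls for multiple imputation. The SAP does not say which prevails.
- *Known to be alive at Day 15.* Neither rule in 6.11.5.1 applies, so 6.2.10 alone supplies the value. At Days 22 and 29 no rule supplies one.

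The plan foresees such subjects. SAP 6.11.1 codes the discharge variable for those who withdraw undischarged before Day 60, and Protocol 8.10 allows vital status to be found by telephone or public records, which gives survival without a WHO score.

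**4. Size per subject.** With 70 placebo and 140 VERU-111 subjects, one reclassified subject moves the rate by 1/70 = 1.4 or 1/140 = 0.7 percentage points. The documents give no count of such subjects.

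**5. Viral load.** Read by parameter, discharge samples from Days 2-8 all map to Day 9, from 7 to 1 days away. Read by visit, Days 2-5 map to Day 3, Day 6 ties, and only Days 7-8 map to Day 9. The content of 'Day 9 only' therefore depends on the undefined term.

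**The case against.** The strongest reply is that this is a general tabulation convention and that endpoint-specific rules would ordinarily override it. Much of that stands:

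- A distant record counts only if nothing nearer exists, so a Day 4 score never displaces an actual Day 15 score.
- For subjects discharged before a WHO visit, 6.2.10 adds nothing. The protocol plans the discharge-day score as the substitute, and SAP 6.11.5.1 and 6.11.5.3 already use it.
- In the WHO 0-1 responder analysis, carry-forward gives the same Day 15 value as mapping an early-termination score.
- Protocol 8.10 asks for every effort to establish vital status, so complete ignorance after an early exit is not the planned case.

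A reader might infer more than the documents support:

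- *That Day 29 is broadly exposed.* Days 26-32 are within the protocol's window, only Days 33-36 exceed it, and a Day 4 record cannot reach Day 29 by this route.
- *That the two viral load time points hold the same data.* They coincide only for a subject whose last sample is also the one closest to Day 9. The separate label suggests that 'Day 9 only' was meant to leave discharge samples out.
- *That a viral load bias can be put in log10 units.* This needs a rate of decline and a discharge imbalance, and the documents give neither.

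The reply does not remove the lack of a stated precedence, the known-alive undischarged withdrawal that only 6.2.10 covers, or the undefined term.

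**Conclusion.** The concern holds for early-termination and unscheduled WHO scores in the analysis of alive without respiratory failure. At Day 15 it rests on the parameter reading and on there being no nearer record; at Day 29 it needs only a missing Day 29 score and a record from Days 33-36. Where vital status is unknown, the result is an unresolved conflict between two SAP sections, not a settled misclassification.

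The reach is limited. Day 60 mortality does not use the mapping, nor do days in ICU and days on mechanical ventilation, the two endpoints in the SAP's Holm procedure. Day 29 is named the key secondary endpoint but is not in that procedure. The total effect cannot be sized. The point is worth correcting because it decides how withdrawn subjects are scored and the correction is cheap; it does not put the primary result in doubt. For viral load, the finding is only that 6.2.10 and the two labels need to be reconciled.

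**What to change.** In SAP 6.2.10:

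1. Define a scheduled time point as one at which that measurement is scheduled.
2. Let an early-termination or unscheduled WHO record fill a visit only within ±3 days. This is the protocol's window for Days 22-60, applied also to Day 15. Apply the same limit to a discharge record dated after the visit. Records outside the limit stay in the listings.
3. Add a tie rule.
4. State that 6.11.5.1 takes precedence for alive without respiratory failure. Visits of undischarged withdrawals with no in-window record are then multiply imputed. Subjects known to be alive at the visit are imputed as alive, so that only their respiratory-failure status is drawn.

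The cost is a few sentences, a programming change and a few more imputed values.

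For viral load, state whether discharge samples taken before Day 9 count as Day 9. This is a trade-off. Counting them mixes sampling times. Excluding them means 'Day 9 only' compares only subjects still in hospital near Day 9, a selection made after randomisation that can differ by arm, and the SAP plans no viral load imputation to offset it. If they are excluded, say so and keep 'Last On-Study' alongside.

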6.3 Conventions

All data listings, summaries, figures and statistical analyses will be generated using SAS version 9.4 or higher¹.

Summaries will be presented by treatment group. Treatment group labels will be displayed as follows:

- VERU-111 9 mg
- Placebo

Listings will be sorted in the following order: treatment group, subject, parameter, and visit unless otherwise stated. All data will be listed, subjects who were not randomized will be displayed after the randomized treatment groups.

Continuous variables will be summarized by the number of non-missing observations, mean, median, standard deviation, and minimum and maximum.

Categorical variables will be summarized by presenting the frequency and percent. Percentages will be based on the number of non-missing observations or the subject population unless otherwise specified. For each variable, all categories will be shown. Zero frequencies (but not the percent) within a category will be presented.

